1.1. Synopsis

Study Title	Assessment study of the AIDAVA prototype which aims to improve the quality of clinical data, for their reuse in clinical care in patients with established cardiovascular diseases, and in clinical research for breast cancer research.											
Rationale	 to curate and publish their personal data in a secure environment, generating an interoperable and reusable personal medical record that can be used in clinical care to improve patient outcomes and to support data driven clinical research. The assessment study will help to determine whether the AIDAVA intelligent virtual assistant is 1. effective in improving data curation and publishing process against existing practices, 2. usable and acceptable by patients - with different levels of health, digital and data literacy - and expert data curators, whenever their input is required, 3. valuable for "data users" such as cardiovascular treating physicians and breast cancer clinical researchers. The efficacy of AIDAVA virtual assistant will be influenced by the quality of the different data curation tools (supporting automation) and by the explainability module (managing the human computer interaction). The study will help identify how these components impact the effectiveness of the device. 											
	The results of the study will be used to inform the exploitation plan of the prototype, and the needed improvement to bring a final device to the market.											
Overall Design	 Three arms, prospective cohort-study involving 30 patients per site, 15 Breast Cancer (BC) and 15 cardiovascular (CVD) + 3 experienced data curator per site based on already collected health data, available across different data sources with 3 arms: one for patients assessing the prototype across the 2 generations⁶, one for the patients assessing the prototype only for a single generation, and one for the expert curators (assessing the prototype across the 2 generations) across 4 epochs (see Figure 1) Epoch 1: 1 week duration, takes place just before deployment and evaluation of Generation 1 (G1) of the prototype; it will allow to gather information from the curator on the current situation. 											
	 Epoch 2: 2 weeks duration per patient during period of July - September 2024: assessment of G1, by ingesting personal health data into the prototype and curating them 											

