1.2. Schema

Figure 1. Schema of the assessment study

1.3. Schedule of Activities (SoA) - see more details in Section 4.

						Inte	rventi	ion Pe	riod V	Veeks (w	ith a wash	out of	16 to	18 mo	nths)					Notes
				Gener	ation	1				Rescreen										
Procedure	before W1)	W1 D1 V1	W1	W1 D5	W2 D1 V2	W2	W2 D5 V3	W3	W4 V4	Develop G2	(< 15 d before W1)	W1 D1 V1	W1	W1 D5	W2 D1 V2	W2	W2 D5 V3	W3	W4 V4	
Check I/E criteria (MD)	xBC	xCVD								(16 to 18	(x)	xCVD								REDCap Form 3
Intro to study (RA)	xBC	xCVD								months)	(x)									SIP (Annex 2)
Sign Informed consent	xBC	xCVD									(x)									On paper
Sign HDI agreement	xBC	xCVD									(x)									On paper
Create HDI account (through AIDAVA)	xBC	xCVD									(x)									
Data extract Hosp/HDI	xBC	xCVD																		After signing ICF
Training the research team	x																			Hospital contact persons, RA, expert curator, MD
Training - on site		x										x								
Training - on line					х										х					
User profile - Health and digital literacy		х										x								REDCap Form 1 (Patient, Curator)
Site monitoring forms		x	x	x	x	x	x	x	x			x	x	x	x	x	x			REDCap Forms 4,5,6,7 (RA)
System Usability Scale							x										x			REDCap Form 8 (Patient, Curator)
Fill in QALY		x										x								Personal Apps
Use BPM device		xCVD	xCVD		xCVD	xCVD				xCVD	xCVD	xCVD		xCVD	xCVD					See Section 6.2

		Intervention Period Weeks (with a washout of 16 to 18 months)															Notes			
	Screen				Gener	ation	1				Rescreen									
Procedure	before W1)	W1 D1 V1	W1	W1 D5	W2 D1 V2	W2	W2 D5 V3	W3	W4 V4	Develop G2	(< 15 d before W1)	W1 D1 V1	W1	W1 D5	W2 D1 V2	W2	W2 D5 V3	W3	W4 V4	
Curate data with AIDAVA		x	x	x	x	x	x					x	x	x	x	x	x			
Curator form - patient							x										x			REDCap Form 11 (Patient)
Curator form - expert	G0						x										x			REDCap Form 9, 10 (Curator)
IPS extract				x			x							x			х			
Extract BC registry				xBC			xBC							xBC			xBC			
Query Federated BC reg. /sec. endpoints				хBС				хBС						хBС				хBС		
SMART risk score (CVD)				xCVD			xCVD							xCVD			xCVD			Manual & auto
Data user form: BC, CVD							x										x			REDCap Form 12,13 (BC), and 14 (CVD)
Feedback to Patient (results + regular info)									x	every 3 mth									x	
Confirm delete data (if dropping out)									x										x	

Figure 2. Schedule of Activities

x = all patients

(x) = only for patients who did not participate to G1 evaluation

xBC = Breast Cancer patient only

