xCVD = Cardio-vascular patients only

2. Introduction

The **AI**-powered **Da**ta Curation **V**irtual **A**ssistant (AIDAVA) project is a 4 year Horizon Europe project (www.aidava.eu). It includes 14 partners (12 EU partners and 2 associated partners). It started in September 2022 and will conclude in August 2026.

Its objective is to develop and test a prototype virtual assistant that will help patients to **curate & publish**⁷ their personal health data, coming from hospital systems and from Health Data Intermediary (HDI)⁸ mediating transfer of GP data, patient health apps and wearables (see detailed list of data sources in Section 10.1. Data Sources). The prototype will maximise automation in the curation and publishing process of personal health data by orchestrating multiple AI technologies; it will request input from the patient - at their level of health and digital literacy - or from expert data curators when automation is not possible. The system will direct the question to the patient or to the expert curator, based on the type of question and the level of experience of the patient.

The end goal is to support patients - or their delegates - to manage all their health data into a longitudinal personal health record, that is interoperable and reusable for multiple purposes, clinical care as well as clinical research. AIDAVA is also intended to support expert curators - within hospitals - to clean and curate hospital's patient data, for further reuse.

There will be 2 generations of the prototype.

- 1. Generation1 (G1), to be deployed by June 2024, will be orchestrating the use of existing tools, open source tools or licensed products.
- Generation2 (G2), to be deployed in December 2025, will improve G1 by integrating novel tools developed in the project. This includes NLP tools - extracting structured data from clinical narratives in local language - and an human-AI module to increase understanding and usability by users with limited health and digital literacy.

To demonstrate the value and the performance of this prototype, we will install these 2 generations of the prototype in a testing environment within the hospital and will perform the assessment study described in this document.

As the system is a prototype, no part of it (including any AI algorithm included in the system) will be used for clinical decision making and cannot be used either as a decision support system for clinicians or as the basis of clinical research.

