3.1. Primary endpoints

The **primary objective** of the assessment study is to compare the acceptance and the performance of the AIDAVA prototype versus existing practice, and between the 2 versions of the prototype. To this end, we propose to measure the following endpoints that will be recorded across sites.

Objective	Primary Endpoints
Metric 1. Evaluate acceptance by end users	Metric definition: Structured questionnaire (adapted from a System Usability Scale with additional questions such as I would recommend AIDAVA to my friend, colleague, or family member I am interested / ready to work with AIDAVA when available on the market I understand the purpose of data curation I am ready to spend the needed time to ensure proper data curation The curation process was perfect/acceptable/too long for me Measurement score (M1) through structured questionnaire (System Usability Scale - form) provided in REDCap
Metric 2. Measure	Metric definition
impact on workload for quality enhancement of data (including quality of the different curation tools)	 Compare time spent in curating data in G0 (current situation) G1 (generation 1 of the prototype) G2 (generation 2 of the prototype). Check the amount of data curated in the average time: are there more data being curated together with the ones needed to support the use case
	 Measurement For estimated time spent in curating (M2.1) User entry in dedicated "Curator form" (RedCap) For curators, when requesting an estimate for G0, it is important to ensure that curated data set have the same level of complexity as for G1 and G2 complexity: Extract a sample (synthetic data ?) to be curated including several data sources; Request existing registry stewards to provide a time to curate data up to insertion into registry (M2.2) System check "active" time of user to answer a query Amount of additional data elements are curated automatically computed (M2.3) How many data elements have been curated automatically by the systems (M2.4) How many data elements have required human interventions and been successful answered by the patients (i.e. answer provided to the question)

Objective	Primary Endpoints
	 (M2.5) How many data elements have required human interventions can not be answered by the patients and are sent to the curators (M2.6) How many data elements send to the curators did not get appropriate answer to finish the curation process

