9.3 Statistical Analyses

Three tests have be retained

- **Paired t-test**: statistical test that compares the means of two related groups, where each subject is measured at two different time points or under two different conditions. It is used to determine if there is a significant difference between the two groups.
- Mann-Whitney U test (unpaired t-test): non-parametric statistical test used to compare the medians of two independent groups. It is often used when the data are not normally distributed or when the sample sizes are small.
- Wilcoxon signed-rank test: non-parametric statistical hypothesis test used to compare two populations with two matched samples.

Primary Endpoint(s) Analysis

The endpoints are defined in Section 9.2 will be used to support the analysis

Computed	Description of measures	Test & meaning (per H1)			
	Population: Expert Curators				
E1	Difference between data points 1 and 2: E1.M2.1△ = M2.1@PDP1 - M2.1@PDP2 E1.M2.2△ = M2.2@PDP1 - M2.2@PDP2	Paired t-test H1: less time spent in curation in G1 than in G0 for expert curators			
E2	Difference between data points 2 and 3: E2.M1-Δ = M1@PDP2 - M1@PDP3	Paired t-test H1: G2 is more usable than G1 for expert curators			
	E2.M2.1∆ = M2.1@PDP2 - M2.1@PDP3 E2.M2.2∆ = M2.2@PDP2 - M2.2@PDP3	H1: less time spent in curation in G2 than in G1 for expert curators			
	Population:	Patients			
P1	Difference in data points 4 and 5 (i.e. difference between G1 and G2 for arm where patients used G1 AND G2)	Paired t-test (effect of system + training/experience from G1)			
	P1.M1- = M1@PDP4 - M1@PDP5	H1: G2 more usable than G1			
	P1.M2.x∆ = M2.x@PDP4 - M2.x@PDP5	H1: G2 requires less time for curation than G1 H1: G2 enables curation with less human intervention than G1			
	P1.M3-∆ = M3@PDP4 - M3@PDP5	H1: G2 provide same or higher quality than G1			
P2	Difference in data points 6 and 7 (i.e. difference between G1 and G2 for arm where patients used G1 OR G2)	Unpaired t-test (effect of system only)			
	P2.M1- = M1@PDP6 - M1@PDP7	H1: G2 more usable than G1			
	P2.M2.x∆ = M2.x@PDP6 - M2.x@PDP7	H1: G2 requires less time for curation than G1 H1: G2 enable curation with less human intervention than G1			
	Ρ2.Μ3-Δ = M3@PDP6 - M3@PDP7	H1: G2 provide same or higher quality than G1			

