10.2 Informed Consent for participation in the evaluation of the AIDAVA prototype tools

(see Annex 2)

10.3 Questionnaires and data entry forms:

10.3.1 Questionnaire to specify the user profile:

These questionnaires will be used to set up the user profile of each subject that will work with the system; it will help the system to interact with the user at the right level taking into account context information and the level of data, health and digital literacy of the user.

Considering that there is an interval of 16 to 18 months between the evaluation of G1 and of G2, users will be requested to fill the question before each evaluation.

Questions to assess medical/health literacy

Health Literacy				
1. Did you receive any medical training or education?	E 🖓	No education	Expert education	reset
2. I often need someone to help me (or need to do some internet research) with reading hospital materials.	H (p	Always	Never	reset
3. I often face difficulties learning about my / a patient's medical condition.) P	Always	Never	reset
4. I know how to find reliable information about medical terms on the Internet.	Ð	Strongly disagree	Strongly agree	reset
5. I am familiar with different units of measurement in the medical context and know their differences (e.g., mmHG and cmHG).	Ð	Strongly disagree	Strongly agree	reset
6. I am familiar with medical standards and terminologies, such as ICD and SNOMED CT.	Ð	Strongly disagree	Strongly agree	reset
Health literacy Score: (0-35)	Ð	18 View e	quation	

Question to assess computer/digital literacy

Digital Literacy			
Digital Literacy			
1. Did you receive any computer science or data science training or education?	Ð	No education Expert education	reset
2. I know how to access the metadata of an electronic file.	H P	Strongly disagree Strongly agree	reset
3. I am always keen on understanding the technical details of innovative solutions.	I) II	Strongly disagree Strongly agree	reset
4. When I use a search engine, I can take advantage of its advanced features.	Ð	Strongly disagree Strongly agree	reset
5. I know how to protect myself from unwanted and malicious online encounters and materials.) E	Strongly disagree Strongly agree	reset
6. When I face a technical problem, I am able to find solutions on the internet.) P	Strongly disagree Strongly agree	reset
Digital literacy Score: (0-35)	•	16 View equation	

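### Literacy scores are collected before each generation, but no analysis in Section 9.3 uses them, so the study question about users of differing literacy gets no result

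*Protocol*

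**What the plan says.** The second of the three questions in the Synopsis rationale, repeated in the introduction to the deliverable, is whether the tool is "usable and acceptable by patients - with different levels of health, digital and data literacy - and expert data curators". Section 2 (Introduction) says G2 adds a human-AI module to "increase understanding and usability by users with limited health and digital literacy".

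The Schedule of Activities (Section 1.3) marks the literacy questionnaire at Week 1 Day 1 of both generations, as "REDCap Form 1 (Patient, Curator". Section 10.3.1 gives a health score and a digital score, each 0-35, and says "users will be requested to fill the question before each evaluation". Section 4.4.1 has curators answer it during pretraining, again before the evaluation. Its only stated purpose is in Section 10.3.1: "These questionnaires will be used to set up the user profile of each subject that will work with the system".

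Section 9.3 opens with "Three tests have be retained": a paired t-test, a Mann-Whitney test (also labelled an unpaired t-test) and a Wilcoxon signed-rank test. It then assigns one of these, or descriptive statistics, to each of E1, E2, P1, P2 and A1 to A4. P2, the comparison of G1-only with G2-only patients, is labelled "effect of system only".

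**The concern.** The protocol poses a question about users of differing literacy and measures literacy in every user, but lists no analysis that connects the two. Each contrast gives one average over all patients in the arm. If G2 helped only the highly literate, the average would still favour G2 and the report would state an overall usability gain. The users for whom part of G2 was designed would not be visible in the result.

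P2 raises a second issue. Its two sides are patients seen only in G1 and patients first seen in G2. Nobody is randomised to these groups: Section 7.2 describes discontinuation after G1 and possible new recruitment for G2. If leavers and newcomers differ in literacy, P2 mixes that difference with the effect of the system, whatever its label says. The measured scores are an available partial remedy.

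**Working it through.** **What each listed analysis uses.**

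| Analysis (Section 9.3) | Method assigned | Literacy, use case or site used? |
|---|---|---|
| E1, E2 | paired t-test | no |
| P1 | paired t-test | no |
| P2, A4 | unpaired t-test | no |
| A1, A2 | descriptive statistics, pooled over patient arms | no |
| A3 | unpaired t-test (signed-rank for M4) | no |

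The hypotheses in Section 9.1 and the analysis sets in Section 9.2 do not mention literacy either.

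**Why the average can mislead.** If a share p of patients gains g on the usability score and the rest gain nothing, the mean change is p × g. That is positive for any g > 0, so the paired test can favour G2 when a share 1 - p has no benefit.

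**The plan's own numbers.** Section 9.4 gives 15 patients × 3 sites × 2 use cases = 90, which agrees with its total. It states no alpha, power, effect size, SD or drop-out rate, so there is no power figure to reproduce. Everything below is assumed: two-sided 5%, a true difference of 0.5 SD, and 10 to 40 patients per side in P2.

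**Precision of the unpaired contrast.** If literacy correlates rho with the outcome, adjustment multiplies the variance by about 1 - rho². The effective difference becomes 0.5/√(1 - rho²): 0.524 at rho = 0.3 and 0.577 at rho = 0.5. Two-sample t-test power, ignoring the degrees of freedom spent:

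| Patients per side | Unadjusted (same as rho = 0) | rho = 0.3 | rho = 0.5 |
|---|---|---|---|
| 10 | 18.5% | 19.9% (+1.4) | 23.1% (+4.6) |
| 20 | 33.8% | 36.5% (+2.7) | 42.9% (+9.1) |
| 30 | 47.8% | 51.5% (+3.7) | 59.4% (+11.6) |
| 40 | 59.8% | 63.9% (+4.1) | 72.2% (+12.4) |

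The formula also assumes literacy is similar on the two sides. If it is not, part of the precision gain is lost, but adjustment then reduces bias. The paired contrasts already remove stable differences between people, so this table does not apply to them.

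**What a literacy analysis could show.** For a regression of the within-patient change on literacy, power by Fisher's z is Φ(atanh(r)·√(n - 3) - 1.96):

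- n = 50, r = 0.4: Φ(0.4236 × 6.856 - 1.96) = Φ(0.94), about 83%
- n = 50, r = 0.3: Φ(0.3095 × 6.856 - 1.96) = Φ(0.16), about 56%
- n = 80, r = 0.3: Φ(0.3095 × 8.775 - 1.96) = Φ(0.76), about 78%
- r = 0.2: about 28% at n = 50 and 43% at n = 80

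A median split within one generation has 80% power for a difference of (1.96 + 0.84) × √(4/n) SD: 0.59 at n = 90, 0.63 at n = 80 and 0.79 at n = 50. The planned data could therefore show moderate to large literacy differences, but not small ones.

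**The case against.** The formal primary objective in Section 3.1 is to "compare the acceptance and the performance of the AIDAVA prototype versus existing practice, and between the 2 versions of the prototype". Literacy appears neither there nor in the hypotheses of Section 9.1, which also rank usability below time and data quality. A reader might infer that a formal objective goes unanswered; the documents do not support that. What goes unanswered is a question in the stated rationale. That part of the objection stands.

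A reader might also infer that the scores are collected for nothing. They are not: they configure how the system addresses each user.

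A third tempting inference is that the study loses much power by not adjusting. Nothing in the protocol gives a literacy-outcome correlation. The 50 to 80 subjects in Section 9.4 are a number assumed sufficient, not a forecast of how many will remain, so no size for the single-generation groups can be derived from it. Section 5.2 also narrows the literacy range by requiring smartphone use and listing literacy as a desirable criterion. Some components, such as the count of automatically curated elements and the computed quality score, may depend little on the user.

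Finally, subgroup tables and covariates are often left to a statistical analysis plan, and the descriptive statistics for A1 and A2 leave room for a breakdown. This has some force, but Section 9.3 does not defer. It names the retained tests and allocates them contrast by contrast, and none of them accepts a covariate.

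**Conclusion.** The point holds for the study question in the rationale: the question is posed, the health and digital scores are collected before each generation, and no listed analysis uses them. Data literacy, also named in the question, has no separate score and cannot be examined separately.

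The precision argument is secondary and conditional. At 0.5 SD and an assumed 10 to 40 per side, the gain is nil at rho = 0, 1 to 4 power points at rho = 0.3, and about 5 to 12 at rho = 0.5. Possible literacy imbalance between the non-randomised G1-only and G2-only patients is a further reason to adjust P2, though adjustment can only partly correct for that selection. Any literacy-by-generation estimate will be imprecise, so it should be read as an estimate with its interval and not as a pass-or-fail test.

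**What to change.** Amend Section 9.3 as follows.

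- **A1 and A2:** report M1 and M2 by health and digital literacy level.
- **P1:** keep the paired estimate. Add a regression of the G2-minus-G1 change in M1 and M2 on the G1 literacy scores, reported with a confidence interval and named as the result that addresses the literacy question. Section 9.3 writes the difference as G1 minus G2, so state the sign used.
- **P2:** replace the unpaired test by a linear model of generation with each patient's first pre-use literacy scores and use case, adding site if numbers allow.
- **A3 and A4, if adjusted:** use one mixed model with a patient random effect and terms for arm, generation and arm-by-generation. Returning patients contribute to both A1 and A2, so a model without a patient term would treat their two records as independent; A4 is the arm-by-generation term. Use the G1 scores for returning patients, because their G2 scores follow training on and use of G1.

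No new data are needed: the scores, site and use case are already on the REDCap forms. The cost is protocol wording, a little more analysis and a few degrees of freedom in P2: three for two scores and use case, and two more for three sites. That matters only if the single-generation groups turn out very small, in which case site should be left out.
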